Appendix 19. Patient Health Questionnaire – 8 items

Protocol ID: _____

CENTER

SUBJECT ID

DATE OF VISIT

- -

dd MMM yyyy

Visit: _____

PATIENT HEALTH QUESTIONNAIRE (PHQ-8)				
 (1) NOT DONE Language Administered:  (44) English for USA				
Over the last 2 weeks , how often have you been bothered by the following problems?	Not at all (0)	Several days (1)	More than half the days (2)	Nearly every day (3)
1. Little interest or pleasure in doing things?				
2. Feeling down, depressed, or hopeless?				
3. Trouble falling or staying asleep, or sleeping too much?				
4. Feeling tired or having little energy?				
5. Poor appetite or overeating?				
6. Feeling bad about yourself—or that you are a failure or have let yourself or your family down?				
7. Trouble concentrating on things, such as reading the newspaper or watching television?				
8. Moving or speaking so slowly that other people could have noticed? Or the opposite—being so fidgety or restless that you have been moving around a lot more than usual?				

PHQ-8 is adapted from PRIME MD TODAY, developed by Drs Robert L. Spitzer, Janet B.W. Williams, Kurt Kroenke, and colleagues, with an educational grant from Pfizer Inc. For research information, contact [name] at [contact]. Use of the PHQ-8 may only be made in accordance with the Terms of Use available of <http://www.pfizer.com>. Copyright ©1999 Pfizer Inc. All rights reserved. PRIME MD TODAY is a trademark of Pfizer Inc.

Appendix 10. Schedule Of Activities48

1. VERSION HISTORY

This is the first amendment of the Statistical Analysis Plan (SAP) for Study B7451013 and is based on the approved protocol dated 06DEC2018.

Table 1. Summary of Major Changes in SAP Amendments

SAP Version	Major Changes	Rationale
2	
Added percent change from baseline in total EASI score and SCORAD score, respectively as endpoints in Section 3.2.3
 
Added responder analyses based on PtGA and DLQI as endpoints in Section 3.3.1
 
Updated the definition of TEAE in Section 3.5.1
 
Added responder analysis based on achieving NRS ≤ 2 as endpoint in Section 3.3.1
	
To evaluate the percent change from baseline in the overall scores of these assessments
 
To further evaluate the results based on these PROs in relation to clinically relevant cutoffs
 
To align with CDISC Safety Rulebook

	Minor Administrative Changes	Rationale
	
Added sentence at the end of FAS definition in Section 4.1, clarifying analysis subset for threshold-based endpoints (see also Sections 6.3.1, 6.4.1, 6.4.2, 6.5.2, 6.5.3, 6.5.5 and 6.6)
 
Added reference to “normal approximation” for confidence interval formula in Section 5.2.1
 
Updated visit window for Screening in Appendix 2
 
Rewrote model expression in Appendix 3
 
Removed frequency of pruritus analyses
	
For further clarification and alignment with previous analyses for similar endpoints
 
For clarification
 
Earlier window left a gap which has been fixed
 
For further clarification and easy readability
 
Align with protocols

2. INTRODUCTION

This SAP provides the detailed methodology for summary and statistical analyses of the data collected in Study B7451013. This document may modify the plans outlined in the protocol; however, any major modifications of the primary endpoint definition or its analysis will also be reflected in a protocol amendment.

2.1. Study Objectives

Study objectives and corresponding endpoints are provided in the Table 2 below.

Table 2. Study Objectives and Endpoints

Primary Objective:
 
To assess the efficacy of PF-04965842 compared with placebo in subjects aged 12 years and older with moderate to severe Atopic dermatitis (AD).
	
Primary Endpoints:
 
The co-primary endpoints:
 
 • Response based on the Investigator’s Global Assessment (IGA) score of clear (0) or almost clear (1) (on a 5-point scale); and a reduction from baseline of ≥ 2 points at Week 12. The baseline will be defined as the IGA score on Day 1 pre-dose. • Response based on the Eczema Area and Severity Index $\geq 75\%$ improvement from baseline (EASI-75) at Week 12. The baseline will be defined as the EASI score on Day 1 pre-dose.

Secondary Objectives:
 
To evaluate the effect of PF-04965842 on additional efficacy endpoints and patient reported outcomes over time in subjects aged 12 years and older with moderate to severe atopic dermatitis.
	
Secondary Endpoints:
 
Key Secondary Endpoints:
 
 • Response based on a ≥ 4 points of improvement in the numerical rating scale (NRS) for severity of pruritus from baseline at Weeks 2, 4, and 12. • Change from Baseline in Pruritus and Symptoms Assessment for Atopic Dermatitis (PSAAD) at Week 12. 
Secondary Efficacy Endpoints:
 
 • Response based on a ≥ 4 points of improvement in the numerical rating scale (NRS) for severity of pruritus from baseline at Week 8. • Time to achieve a ≥ 4-point improvement in the numerical rating scale (NRS) for severity of pruritus from baseline. • Response based on the EASI-75 at all scheduled time points except Week 12. • Response based on the IGA for clear (0) or almost clear (1); and ≥ 2 points reduction from baseline at all scheduled time points except Week 12. 
Other Efficacy Endpoints
 
 • Response based on a $\geq 50\%$ and $\geq 90\%$ improvement in the EASI total score (EASI-50 and EASI-90) at all scheduled time points. • Change from baseline in the percentage Body Surface Area (BSA) affected at all scheduled time points. • Response based on a $\geq 50\%$ and $\geq 75\%$ improvement in Scoring Atopic Dermatitis (SCORAD50, SCORAD75) from baseline at all scheduled time points. • Change from baseline at all scheduled time points in SCORAD subjective Visual Analogue Scale (VAS) assessments of itch and sleep loss. 
CCI [REDACTED]
 
[REDACTED]
 
[REDACTED]

	
and at all other scheduled time points.
 
 • Change from baseline at Week 12 in Patient-Oriented Eczema Measure (POEM) and at all other scheduled time points. • Change from baseline of Patient Global Assessment (PtGA) at Week 12 and at all other scheduled time points. • Change from baseline of EuroQol Quality of Life 5-Dimension 5-Level Scale (EQ-5D-5L) or EuroQol Quality of Life 5-Dimension Youth Scale (EQ-5D-Y) at Week 12 and at all other scheduled time points. • Change from baseline of Functional Assessment of Chronic Illness Therapy Fatigue Scale (FACIT-F) or Pediatric FACIT-F (Peds-FACIT-F) at Week 12 and at all other scheduled time points. • Change from baseline of Short Form-36 (SF-36), acute at Week 12 and at all other scheduled time points. • Change from baseline of Work Productivity and Activity Impairment Questionnaire: Atopic Dermatitis (WPAI:AD) at Week 12 and at all other scheduled time points. Response based on at least 4 points improvement in the frequency of pruritus numerical rating scale (NRS) from baseline at all scheduled time points.¹ • Time to achieve at least 4 points improvement in the frequency of pruritus NRS scale from baseline.¹
Safety Objective	Safety Endpoints

To evaluate the safety and tolerability of PF-04965842 in subjects aged 12 years and older with moderate to severe atopic dermatitis following 12 weeks of treatment.
	
 • Incidence of Treatment Emergent Adverse Events (TEAEs). • Incidence of Serious Adverse Events (SAEs) and Adverse Events (AEs) leading to discontinuation. • The incidence of clinical abnormalities and change from baseline in clinical laboratory values, Electrocardiogram (ECG) measurements, and vital signs.

¹ The frequency of pruritus numerical rating scale (NRS) is listed as an endpoint in the protocol but will not be analyzed. This is because, after its selection as an endpoint in the study protocol, evidence was uncovered that suggested the instrument did not have sufficient content validity. Specifically, the response scale for the frequency of pruritus NRS was found not to be ideally representative of the range of frequency levels from the perspective of the target population based on qualitative research. Data generated from this measure would not be easily interpretable. Therefore, the endpoint will not be analyzed.

[figure not shown]
PK Objectives	PK Endpoint
To evaluate the pharmacokinetics (PK) of PF-04965842 in subjects aged 12 years and older with moderate to severe atopic dermatitis following 12 weeks of treatment.	
• Population PK characterization in subjects aged 12 years old and above with moderate to severe atopic dermatitis.
CCI [REDACTED]	■ [REDACTED]
[REDACTED]	■ [REDACTED] ■ [REDACTED]
[REDACTED]	■ [REDACTED] • [REDACTED] • [REDACTED]

2.2. Study Design

This is a randomized, double-blind, placebo-controlled, parallel-group, Phase 3 study to evaluate the efficacy and safety of PF-04965842 monotherapy in subjects aged 12 years and older with moderate to severe AD and a body weight ≥ 40 kg. The treatment duration is 12 weeks. Subjects will be screened within 28 days prior to the first dose of investigational product to confirm that they meet the subject selection criteria for the study. A total of approximately 375 subjects will be enrolled from approximately 115 sites located globally. A study design schematic is presented in

Figure 1.

Figure 1. Study Design Schematic

* At Week 12, eligible subjects may enter a long-term extension study; all other subjects enter the 4 week follow-up period

Qualified subjects completing the 12-week treatment period of the study will have the option to enter a long-term extension (LTE) study B7451015. Subjects discontinuing early from treatment, or who are otherwise ineligible for the LTE study, will undergo a 4-week follow-up period in B7451013.

Subjects who have chronic moderate to severe AD as defined per the inclusion criteria and have a documented history of inadequate response or intolerance to treatment with topical AD medications will be randomized in a 2:2:1 ratio to receive 200 mg PF-04965842 (N=150) or 100 mg PF-04965842 QD (N=150), or matching placebo (N=75) from Day 1. Randomization will be stratified by baseline disease severity (moderate [IGA=3] and severe [IGA=4] AD) and age (age <18 and ≥18 years). Investigators, subjects, and the sponsor study team will be blinded as to treatment group.

A full schedule of activities for the study is provided in [Appendix 11](#).

Study Treatments

- Doses of PF-04965842 will be 200 mg or 100 mg taken QD orally, or matching placebo;
- Treatment duration will be 12 weeks;

Sample Size Determination

Sample size for the study was based on the co-primary endpoints. A sample of 150 subjects randomized to PF-04965842 200 mg QD, 150 subjects randomized to PF-04965842 100 mg QD and 75 subjects randomized to placebo would provide at least 95% power to detect a difference in IGA response rate of at least 20% between PF-04965842 200 mg QD (or

PF-04965842 100 mg QD) and placebo, assuming the placebo response rate is 6% at Week 12. Furthermore, this will also provide at least 99% power to detect a difference in EASI-75 response rate of at least 30% between PF-04965842 200 mg QD (or PF-04965842 100 mg QD) and placebo, assuming the placebo response rate is 15% at Week 12.

The Type-I error for testing each individual co-primary endpoint was set at 5%. Since both endpoints are co-primary, the study will meet its primary endpoint only if both hypotheses (corresponding to each co-primary endpoint) are rejected. Therefore, the Type-I error rate remains controlled at 5% for testing the primary endpoints. The power to reject both hypotheses when a true difference exists (alternative hypothesis is true) could be at least 94% depending on the correlation between the endpoints.

3. ENDPOINTS AND BASELINE VARIABLES: DEFINITIONS AND CONVENTIONS

3.1. Primary Endpoints

The co-primary efficacy endpoints are:

- Response based on the IGA score of clear (0) or almost clear (1); and a reduction from baseline of ≥ 2 points at Week 12;
- Response based on the EASI $\geq 75\%$ improvement from baseline (EASI-75) at Week 12.
- Detailed descriptions of how the IGA and the EASI scores are derived are provided in [Appendix 5](#) and [Appendix 6](#) respectively.

3.2. Secondary Efficacy Endpoints

3.2.1. Key Secondary Efficacy Endpoints

The key secondary efficacy endpoints are:

- Response based on ≥ 4 points improvement from baseline in the pruritus NRS (NRS4) for severity at Weeks 2, 4, and 12;
- Change from baseline in PSAAD at Week 12.
- Detailed descriptions of how the pruritus NRS and PSAAD scores are derived are provided in [Appendix 8](#) and [Appendix 10](#), respectively.

3.2.2. Secondary Efficacy Endpoints

The secondary efficacy endpoints are:

- Response based on NRS4 for severity at all time points other than Weeks 2, 4 and 12;
- Time to achieve a ≥ 4 -point improvement from baseline in the numerical rating scale (NRS) for severity of pruritus;

- Response based on the EASI-75 at all scheduled time points except Week 12;
- Response based on the IGA for clear (0) or almost clear (1); and ≥ 2 points reduction from baseline at all scheduled time points except Week 12.

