
CCI

Endpoints

Primary Efficacy Endpoints:

- Response based on the Investigator's Global Assessment (IGA) score of clear (0) or almost clear (1) (on a 5-point scale) and a reduction from baseline of ≥ 2 points at Week 12. The baseline will be defined as the IGA score on Day 1 pre-dose;
- Response based on the Eczema Area and Severity Index 75% improvement from baseline (EASI-75) response at Week 12. The baseline will be defined as the EASI score on Day 1 pre-dose.

Key Secondary Efficacy Endpoints:

- Response based on at least 4 points improvement in the severity of pruritus numerical rating scale (NRS) from baseline at Weeks 2, 4, and 12;
- Change from Baseline in Pruritus and Symptoms Assessment for Atopic Dermatitis (PSAAD) total score at Week 12.

Secondary Efficacy Endpoints:

- Response based on at least 4 points improvement in the severity of pruritus numerical rating scale (NRS) from baseline at all scheduled time points other than Weeks 2, 4 and 12;
- Time to achieve at least 4 points improvement in the severity of pruritus NRS scale from baseline by Day 15;
- Response based on the EASI-75 at all scheduled time points except Week 12;
- Response based on the IGA of clear (0) or almost clear (1) and ≥ 2 point reduction from baseline at all scheduled time points except Week 12.

Other Efficacy Endpoints:

- Response based on a $\geq 50\%$ and $\geq 90\%$ improvement in the EASI total score (EASI-50 and EASI-90) at all scheduled time points;
- Change from baseline in the percentage Body Surface Area (BSA) affected at all scheduled time points;
- Response based on a $\geq 50\%$ and $\geq 75\%$ improvement in Scoring Atopic Dermatitis (SCORAD) (SCORAD-50, SCORAD-75) from baseline at all scheduled time points;
- Change from baseline at all scheduled time points in SCORAD-subjective assessments of itch and sleep loss.

CCI [REDACTED]

[REDACTED]

[REDACTED]

[REDACTED]

[REDACTED]

CC
I

[REDACTED]

[REDACTED]

[REDACTED]

[REDACTED]

[REDACTED]

[REDACTED]

[REDACTED]

Safety Endpoints:

- Incidence of treatment emergent adverse events;
- Incidence of Serious Adverse Event (SAE)s and Adverse Event (AE)s leading to discontinuation;
- The incidence of clinical abnormalities and change from baseline in clinical laboratory values, electrocardiogram (ECG) measurements, and vital signs.

Pharmacokinetic Endpoint:

- Population PK characterization in subjects aged 12 years and older with moderate to severe atopic dermatitis.

CCI

[REDACTED]

[REDACTED]

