- s. Site staff is to administer the C-SSRS, SBQ-R and PHQ-8 to all subjects at screening and score immediately. Subjects who have recent or active suicidal ideation or behavior or clinically significant depression will be excluded from the study or discontinued from the study per [Section 4.2](#), [Section 7.5.1](#), [Section 7.5.2](#) and [Section 7.5.3](#). For subjects meeting exclusionary results on the C-SSRS, SBQ-R and PHQ-8, it is recommended the subject's primary care physician (PCP) should be informed, and the subject referred to a mental health professional, either by the PCP or the investigator according to their usual practice.
- t. For subjects at selected study sites, photographs of treated AD will be obtained. Photographs will be utilized for illustrative purposes and not evaluated as an endpoint (see [Section 7.7.5](#)).
- u. Pruritus Numerical Rating Scale (NRS) and Night Time Itch Scale will be assessed using an eDiary, daily during the screening period and from Day 1 to 15. After Day 15, the pruritus NRS and Night Time Itch Scale will be completed only on study visit days in the eDiary. At the Screening visit, site staff will dispense the ePRO device and review instructions for completion of the subject eDiary for the NRS and Night Time Itch Scale. At every visit, the study coordinator will review the eDiary for completeness and counsel the subject on how to complete the items in the daily eDiary, if needed.
- v. Pruritus and Symptoms Assessment for Atopic Dermatitis (PSAAD) will be conducted to assess the severity and frequency of pruritus, symptoms and sleep collected daily in a subject e-diary during the screening period and from Day 1 through the End of Study visit in selected countries (See [Section 7.8.8](#)). At the Screening visit, site staff will dispense the ePRO device and review instructions for completion of the subject eDiary for the PSAAD questionnaire. Subjects will be asked to record their assessment in their eDiary once a day before taking the investigational product. At every visit, the study coordinator will review the eDiary for completeness and counsel the subject on how to complete the items in the daily eDiary, if needed.
- w. DLQI will be completed by adult subjects only. Adolescents 12-17 years of age will complete the CDLQI instead.
- x. SF-36v2 and WPAI:AD will be completed by adult subjects only. Adolescents 12-17 years of age will not complete these assessments.

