6.2.3. Visit 4, Day 15/Week 2 (±1 day)

- Administer PROs including PtGA, DLQI (or CDLQI), POEM, HADS and EQ-5D-5L (or EQ-5D-Y);
- Adolescents 12-17 years of age will complete the CDLQI instead of the DLQI and the EQ-5D-Y instead of the EQ-5D-5L;
- Review pruritus NRS, Night Time Itch Scale, and PSAAD completion (in selected countries) and review eDiary procedures with subject as necessary. Instruct subject that pruritus NRS and Night Time Itch Scale will now be completed only at visits on site and in the eDiary and will no longer be completed on a daily basis at home;

- Urine pregnancy test (female subjects of childbearing potential, including adolescents aged 12 years and older, regardless of whether they have experienced menarche). A negative urine pregnancy test must be obtained prior to dosing with the investigational product;
- Administer investigational product at clinic;
- Perform a single 12-lead electrocardiogram (ECG);
- Conduct targeted physical examination;
- Obtain samples for laboratory testing: serum chemistry, hematology (including coagulation panel), and urinalysis;
- Conduct clinical evaluations including IGA, SCORAD, EASI and BSA (calculated in the EASI);
- Photography of AD lesions (at selected sites; [Section 7.7.5](#));
- Obtain vital signs including pulse rate, blood pressure, respiratory rate and oral or tympanic temperature (after at least 5 minutes of rest). Vital signs must be performed at least 1 hour following administration of investigational product;
- Assess need for contraception and adherence to applicable lifestyle requirements ([Section 4.4](#)). Establish willingness and ability to comply with lifestyle requirements going forward in the study;
- Review any changes in the subject's concomitant medications and treatments information;
- Review eDiary to assess completion;
- Perform drug accountability procedures;
- Assess and record any Adverse Events since the last visit.

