6.2.5. Visit 6, Day 43/Week 6 (± 3 day)

- Call subject and confirm compliance with daily completion of PSAAD (in selected countries);
- Verbally confirm subject has been compliant with study dosing and entry in the eDiary. Review eDiary procedures with subject as necessary;

- Review any changes in the subject's concomitant medications and treatment information;
- Assess need for contraception and adherence to applicable lifestyle requirements ([Section 4.4](#)). Establish willingness and ability to comply with lifestyle requirements going forward in the study;
- Assess and record any Adverse Events since the last visit.

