5.2.5. Analyses of Time to Event Data

For a subject who experiences the event, the time to event will be the study day corresponding to the actual date of the event or the earliest visit date at which the subject has already experienced the event. For all subjects who have not experienced the event, their time to event will be right censored at the last available measurement time (or visit) used to define whether the subject experienced the associated event.

Time-to-event endpoints will be summarized using the Kaplan-Meier method and estimated survival curves will be displayed graphically. Graphs will describe the number of patients at risk over time. The median and quartiles will be estimated by the Kaplan-Meier method and 95% CI for the median and quartiles will also be provided.

The log-rank test (stratified using randomization strata) p-value will be used for comparing time to event data between each active group and the placebo group.

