6.4.2. Time to Achieve NRS4 for severity

- Summary: Time to achieve a ≥ 4 -point improvement in the pruritus NRS for severity from baseline:
- Population: Subjects from the FAS with a baseline NRS score for severity ≥ 4 .
- Statistical Method: Analyses for Time to Event Data in [Section 5.2.5](#).
- Missing Data: See [Section 5.3.3](#).

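### The SAP omits the protocol's Day 15 limit on time to NRS4, so any median or quartile falling after Day 15 becomes a clinic visit date

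*SAP*

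**What the plan says.** **Protocol.** The Protocol Summary and Table 1 both list the secondary endpoint as "Time to achieve at least 4 points improvement in the severity of pruritus NRS scale from baseline by Day 15". The Schedule of Activities, footnote u, has the pruritus NRS completed in the eDiary "daily during the screening period and from Day 1 to 15". It continues: "After Day 15, the pruritus NRS and Night Time Itch Scale will be completed only on study visit days in the eDiary". Section 6.2.3 (Week 2 visit) tells subjects that the scale "will now be completed only at visits on site and in the eDiary". The Week 6 contact in Section 6.2.5 is a telephone call, and its diary item is "Call subject and confirm compliance with daily completion of PSAAD (in selected countries"; the NRS is not mentioned.

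**SAP.** Section 3.2.2 describes the time to a 4-point or greater "improvement from baseline in the numerical rating scale (NRS) for severity of pruritus", without a Day 15 limit. Table 2 in Section 2.1 also omits it, as does Section 6.4.2, which refers only to an "improvement in the pruritus NRS for severity from baseline". Section 5.2.5 dates an event at its actual date "or the earliest visit date at which the subject has already experienced the event". It then asks for Kaplan-Meier medians and quartiles with 95% confidence intervals and a stratified log-rank test. Sections 5.2.5 and 5.3.3 censor subjects without the event at their last available measurement. No interval-censored method is given.

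**The concern.** The protocol's limit matches the data collection: it ends the endpoint when daily scoring ends. Without it, the Kaplan-Meier curve runs on to Week 12 over three widely spaced readings, and the SAP treats the visit date as the response date. A median or quartile in that stretch reflects the visit schedule as much as the onset of itch relief, and it can only err towards being late.

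The effect can differ between arms. A fast arm whose median falls by Day 15 is read from daily scores, while a slower arm's median is rounded up to a visit. The gap between two reported medians can then look wider than it is.

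The departure is also unexplained in the readable text. For another protocol endpoint that it drops, frequency of pruritus, the SAP gives a footnote to Table 2 with reasons. Nothing comparable covers this change.

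**Working it through.** The documents give no median, event count or NRS4 response rate for this endpoint, so there is no plan figure to reproduce. The check is arithmetic on the visit schedule.

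**Inputs**
- Daily NRS to Day 15, then on-site visits only (Schedule of Activities, footnote u; Protocol 6.2.3).
- Later on-site visits: Day 29 ±2, Day 57 ±3 and Day 85 ±3; the Week 2 visit is Day 15 ±1.
- No NRS at the Day 43 call (Protocol 6.2.5). Week 16 data go to listings only unless noted otherwise (SAP 6).
- SAP Appendix 1 shows the same grid for change in NRS severity: Days 1 to 15, then Weeks 4, 8 and 12.

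**Greatest lateness on nominal days** = next reading − (previous reading + 1)
- Day 15 to 29: 29 − 16 = 13 days
- Day 29 to 57: 57 − 30 = 27 days
- Day 57 to 85: 85 − 58 = 27 days

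If onset is spread evenly within a gap, the average lateness is (0 + 13)/2 = 6.5 days, then (0 + 27)/2 = 13.5 days in each later gap.

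**With visit windows** (previous visit as early as allowed, next as late as allowed)
- (29 + 2) − (15 − 1) − 1 = 16 days, if daily scoring stops at a Day 14 visit
- (57 + 3) − (29 − 2) − 1 = 32 days
- (85 + 3) − (57 − 3) − 1 = 33 days

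These are extremes for one subject's recorded time. A median would reach them only if visits clustered that way.

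**With a missed reading** (nominal days)
- Week 4 missed: Day 16 is recorded as Day 57, 57 − 16 = 41 days late.
- Week 8 missed: Day 30 is recorded as Day 85, 85 − 30 = 55 days late.

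SAP 5.3.1 makes this a practical matter: a device error left NRS data uncollected from several subjects at Week 2 and later visits. Binary NRS endpoints get multiple imputation for such gaps; time to NRS4 uses observed data (SAP Appendix 1).

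**Effect on the median.** Moving each event to the next reading preserves the order of events, so a median at or before Day 15 stays put and a later one moves to a visit day. A simulation illustrates this (assumptions: 150 subjects, exponential onset, response sustained to the next visit, no dropout; 300 repetitions).

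| Assumed true median (day) | Typical reported median, nominal visits | Typical reported median, visits spread over windows |
|---|---|---|
| 8 | 8 | 8 |
| 14 | 14 | 14 |
| 20 | 29 | 29 |
| 30 | 57 | 54 |
| 45 | 57 | 58 |
| 60 | 85 | 82 |

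Two arms with assumed medians of 14 and 30 differ by 16 days; on nominal visits they would be reported as 14 and 57, a difference of 43. The onset times are assumptions, not trial data. The gap arithmetic does not depend on them.

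**The case against.** The SAP may modify the protocol's plan. Both documents require a protocol amendment only for major changes to the primary or co-primary endpoints. SAP Table 1 records changes between SAP versions, so its silence does not show that a change was concealed. That stands; what remains is that the SAP nowhere explains the difference.

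The 12-week curve contains the protocol's quantity: up to Day 15 it uses the same daily data, and nothing is lost. That is true of the curve, but the headline median or quartile may still be read from the part beyond Day 15.

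The dating rule is stated openly and all arms share one schedule. A reader might infer that the treatment comparison is biased. The documents do not support that: a common grid does not itself favour an arm in the log-rank test. The weakness lies in the estimated times.

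Early-termination visits add some NRS readings, and a transient response between visits would not be seen at the next one. Both are fair qualifications: the lateness figures describe subjects on schedule whose response lasts. A reader might also infer growing bias from dropout, but no dropout rate is given, so that cannot be sized.

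Finally, this is a non-key secondary endpoint tested at a nominal 5%, and NRS4 is also analysed as proportions at Weeks 2, 4, 8 and 12. That limits the stakes.

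**Conclusion.** The point holds for a defined part of the results. The protocol and SAP state different endpoints, the SAP does not explain why, and its event dating turns any median or quartile after Day 15 into a visit date. On nominal days that is at most 13 days late between Weeks 2 and 4 and at most 27 days late afterwards, assuming the response is sustained to the visit and no reading is missed.

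Two stronger readings are tempting and should be resisted.
- That the reported medians will be late. Only those beyond Day 15 are affected, and without NRS4 rates the documents do not show whether any arm's median lies there.
- That 27 days is a ceiling. Visit windows allow 33 days, and a missed Week 8 reading allows 55.

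No primary or key secondary conclusion depends on this endpoint. It should still be corrected, because it is a named secondary endpoint and the correction is cheap.

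**What to change.** Restore the Day 15 limit in SAP 2.1 (Table 2), 3.2.2 and 6.4.2. Censor subjects who have not responded at their last available NRS reading on or before Day 15. Do not censor all non-achievers at Day 15 itself: that would keep early dropouts, and subjects whose late diary entries were lost, at risk without data, against SAP 5.2.5 and 5.3.3.

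If the 12-week version is kept as a supplement, estimate it with a method that treats each event after Day 15 as lying between two readings, and state that it departs from the protocol.

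The cost is SAP wording and a small program change. The downside is that an arm's median may be reported as not reached by Day 15. The device error begins at Day 15, so the limit removes most, but not all, exposure to it.
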